## 8.4. Demographic data and baseline characteristics, including medical history and therapies

Descriptive analyses will be provided by cohorts, subgroups and overall on the mITT.

Number and percentage of patients included in each subgroups defined in [Section 5](#) will be provided by cohorts and overall on the mITT.

Medical and surgical history will be analyzed by MedDRA SOC and PT. Medical and surgical history will be tabulated with number of history, number and percentage of patients with at least one history classified by SOC and PT.

Prior therapies and concomitant treatments will be tabulated with number of treatments, number and percentage of patients with at least one treatment classified by therapeutic class (ATC2) and preferred name.

## 8.5. Extent of exposure

Descriptive analyses will be provided by cohorts, subgroups and overall on the mITT.

The same analyses will be provided according to expected dose:

- Adult patients and children with body weight equal to or above 35 kg (i.e. who should took 24 tablets)
- Children with body weight of at least 20 kg and below 35 kg (i.e. who should took 12 tablets)

## 8.6. Analysis of the primary endpoint

### Primary analysis

A descriptive analysis of the primary efficacy endpoint with the 95% exact Clopper-Pearson confidence intervals will be provided on the mITT (overall).

### Sensitivity analysis

A descriptive analysis of the primary efficacy endpoint with the 95% exact Clopper-Pearson confidence intervals will be provided on the Evaluable patients set and PP set (overall).

### Secondary analysis

A descriptive analysis of the primary efficacy endpoint with the 95% exact Clopper-Pearson confidence intervals will be provided by cohorts and by subgroups on the mITT.

## 8.7. Analysis of the secondary endpoints

### 8.7.1. Analysis of the endpoint at 12 months

The endpoint at 12 months will be analysed as described for the primary endpoint (see above [Section 8.6](#): “primary”, “sensitivity” and “secondary” analyses).

### 8.7.2. Analysis of failures

Analysis of failures will be provided on the mITT (overall).

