4.3. Eligibility Criteria for Out-patient Treatment

To be eligible for treatment on an out-patient basis, the patient must fulfil all of the following criteria:

- Accepting to be treated on an out-patient basis;
- Karnofsky Performance Status > 50%;
- Good understanding of the method of administration of fexinidazole by the patient and/or caregiver (checked using a questionnaire at the time of dispensing fexinidazole);
- Residing close to the investigational centre, i.e. at most one hour by road and/or boat, during the treatment period*;
- Easily reachable during the treatment period;
- No medical or psychiatric contraindications for treatment as out-patient;
- No pregnancy or breastfeeding;

Confidential Page 27 of 83

- No neurological symptoms.
- * The patient (and caregiver) is permitted to reside in a place different from his/her main place of residence during the treatment period.

5. Study Treatment

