## 5. ANALYSIS SETS AND SUBGROUPS

The analysis sets are the following.

- **Screened HAT positive patients:** all HAT positive patients who signed the informed consent.
- **Intent-to-treat (ITT) population:** all patients included in the study, regardless of whether or not they took the IMP (but the treatment unit was provided to the outpatient);
- **Modified intent-to-treat (mITT) population:** all patients who took at least one tablet of fexinidazole;
- **Evaluable patients:** patients included in the mITT and excluding:
  - Patients lost to follow-up at 18 months (for primary efficacy endpoint and secondary efficacy outcome at 18 month), patients lost to follow-up at 12 months (for secondary efficacy outcome at 12 month), except those who were a failure before being lost to follow-up.
  - Patients with no post-treatment lumbar puncture
  - Patients who died for reasons clearly unrelated to efficacy or safety or disease evolution (\*\*).
- **Per protocol (PP):** all patients who completed the study in accordance with the protocol with no major violations (cf. [Section 8.2](#)) that could interfere with the efficacy evaluation. An out-patient who did not take any tablet of the IMP or with a compliance below 75% of the expected number of tablets is not per protocol unless it is due to lack of tolerance. Premature withdrawal from the study due to treatment inefficacy or intolerance will not be considered as a protocol violation.

Two study cohorts are defined:

- **Inpatients:** patients treated in hospital,
- **Outpatients:** patients treated on an outpatient basis. Note that outpatients that would require hospitalization (for any reason) will be analyzed according to their initial cohort (i.e. as “outpatients”).

The following subgroups are defined according to the stage and severity of disease at inclusion:

- Stage 1
- Intermediate stage
- Stage 1 + Intermediate stage
- Stage 2
- WBC in CSF  $\leq$  100 /  $\mu$ L
- 100 < WBC in CSF  $\leq$  400 /  $\mu$ L
- WBC in CSF  $>$  400 /  $\mu$ L

For the analysis, these subgroups will be calculated as described in Table 1. Subgroups analyses are specified in [Section 8](#).

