#### Description:

A listing of failures will provide for each failure:

- The time to failure (since the first treatment administration)
- Signs of failure observed: WBC in CSF >20/ $\mu$ L, death (cause if known), presence of trypanosomes in blood or lymph, rescue medication and LTFU
- Number of WBC in CSF at inclusion
- WBC in CSF at inclusion classified as follows:  $\leq$  100, 100-400 and  $>$  400/ $\mu$ L
- Presence of trypanosomes in CSF
- Presence of the following symptoms at inclusion: sleepiness, prurit, tremor, asthenia and headache
- Number of tablets left over at the end of treatment.

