#### Statistical modeling: logistic regression

- Model 1: the failure rate will be related to the  $\log_e$  of the number of WBC in CSF (/ $\mu$ L) at inclusion.
- Model 2: the failure rate will be related to the compliance (number of tablets left over at the end of treatment)
- Model 3: the failure rate will be related to the score equal to the sum of weighted symptoms at inclusion (5 points if sleepiness observed at entry, 4 points for prurit, 3 points for tremor, 2 points for asthenia and 1 point for headache).
- Model 4: the failure rate will be related to the presence of a symptom score of 12 or more (see model 3).

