### **2.2.2 Analysis of failures**

Statistical Table 2.2.2.1: Logistic regression: Model 1 – all patients (mITT)

Statistical Table 2.2.2.2: Logistic regression: Model 2 – all patients (mITT)

Statistical Table 2.2.2.3: Logistic regression: Model 3 – all patients (mITT)

Statistical Table 2.2.2.4: Logistic regression: Model 4 – all patients (mITT)

Statistical Table 2.2.2.5: Logistic regression: Model 5 – all patients (mITT)

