## 10. KEY DERIVED VARIABLES

### 10.1. Outcome at 18 months

Derivation algorithm for stage 1 and intermediate stage (Month 18)	Derivation algorithm for stage 2 (Month 18)
Patient is dead (any reason of death and any time between drug intake and M18) $\Rightarrow$ YES $\Rightarrow$ Failure (stop) $\Downarrow$ NO (patient alive) $\Downarrow$	Patient requires rescue medication for HAT at M18 or required it before (between drug intake and M18) $\Rightarrow$ YES $\Rightarrow$ (definitive) Failure (stop) $\Downarrow$ NO rescue medication so far $\Downarrow$
Evidence of trypanosomes in any body fluid between drug intake and M18 visit $\Rightarrow$ YES $\Rightarrow$ (definitive) Failure (stop) $\Downarrow$ NO observed trypanosomes $\Downarrow$	Patient Lost to follow-up at M18 (no survival information at M18 and later) $\Rightarrow$ YES $\Rightarrow$ Failure (Stop) $\Downarrow$ NO (the patient is not lost to follow-up) $\Downarrow$
Non-haemorrhagic lumbar puncture at M18 and WBC in CSF at M18 >20 cells $\Rightarrow$ YES $\Rightarrow$ Failure (stop) $\Downarrow$ NO (WBC in CSF at M18 $\leq$ 20 cells or no reliable data concerning WBC in CSF at M18) $\Downarrow$	Non-haemorrhagic lumbar puncture at M18 and WBC in CSF <math>\leq</math>20 cells $\Rightarrow$ YES $\Rightarrow$ Success (stop) $\Downarrow$ NO (haemorrhagic CSF sample or no lumbar puncture at M18 for any reason) $\Downarrow$
No lumbar puncture at M18 or no reliable count of WBC in CSF at M18 but reliable number of WBC in CSF reported later (M24 or other additional visit) $\Rightarrow$ YES $\Rightarrow$ WBC in CSF >20 $\Rightarrow$ Failure (Stop) $\Rightarrow$ YES $\Rightarrow$ WBC in CSF <math>\leq</math>20 $\Rightarrow$ Success (Stop) $\Downarrow$ NO (No lumbar puncture at M18 and no later reliable count of WBC in CSF) $\Downarrow$	Patient has clinical signs or symptoms at M18 evoking a failure $\Rightarrow$ YES $\Rightarrow$ Failure (stop) $\Downarrow$ NO (no clinical signs or symptoms evoking a relapse at M18) $\Downarrow$

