## 10.2. Outcome at 12 months

Derivation algorithm for stage 1 and intermediate stage (Month 12)	Derivation algorithm for stage 2 (Month 12)
Patient is dead (any reason of death and any time between drug intake and M12) ⇒ YES ⇒ Failure (stop)	
↓ NO (patient alive) ↓	
Patient requires rescue medication for HAT at M12 or before ⇒ YES ⇒ Failure (stop)	
↓ NO rescue medication so far ↓	
Evidence of trypanosomes in any body fluid at M12 or between drug intake and M12 visit ⇒ YES ⇒ (definitive) Failure (stop)	
↓ NO observed trypanosomes so far ↓	
Patient Lost to follow-up at 12M (no survival information at M12 and later) ⇒ YES ⇒ Failure (Stop)	
↓ NO (the patient is not lost to follow-up)	
↓ Non-haemorrhagic lumbar puncture at M12 and WBC in CSF >20 cells ⇒ YES ⇒ Failure (stop)	↓ Non-haemorrhagic lumbar puncture at M12 and WBC in CSF at M12 ≥ 50 cells ⇒ YES ⇒ Failure (stop)
↓ NO (WBC in CSF at M12 ≤ 20 cells or no reliable count of WBC in CSF at M12) ↓	↓ NO (WBC in CSF at M12 < 50 cells or no reliable count of WBC in CSF at M12)
Non-haemorrhagic lumbar puncture at M12 and WBC in CSF at M12 ≤20 cells ⇒ YES ⇒ Success (Stop)	Non-haemorrhagic lumbar puncture at M12 and WBC in CSF at M12 ≤20 cells ⇒ YES ⇒ Success (Stop)
↓ NO (no reliable count of WBC in CSF at M12) ↓	↓ NO (no reliable count of WBC in CSF at M12)
↓ ↓	Non-haemorrhagic lumbar puncture at M12 with WBC in CSF <50 but >20 and increase of WBC in CSF with respect to M6 or sign and symptoms evoking a failure ⇒ YES ⇒ Failure (stop)
↓ ↓	↓ NO (patient did not meet at least one of the previous criteria at M12)
↓ ↓	Non-haemorrhagic lumbar puncture at M12 with WBC in CSF <50 but >20 cells and decrease of WBC in CSF with respect to M6 and no signs and symptoms evoking a failure (success at M18 if status is available) ⇒ YES ⇒ Success (stop)
↓ ↓	↓ NO (patient did not meet at least one of the previous criteria)

Derivation algorithm for stage 1 and intermediate stage (Month 12)	Derivation algorithm for stage 2 (Month 12)

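### The failure models in SAP 8.7.2 are fitted only on the mITT, so they mix treatment failure with outcomes not known to be treatment failures; Model 4 also probably has no out-patients in its exposed group

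*SAP*

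**What the plan says.** SAP 8.7.2 sets the population for the failure listing and the models: "Analysis of failures will be provided on the mITT (overall)". The table list in SAP 9.1 repeats it for every model, for example "Statistical Table 2.2.2.1: Logistic regression: Model 1 – all patients (mITT)", and lists no version on another set. SAP 5 defines the mITT as "all patients who took at least one tablet of fexinidazole", so patients who are later lost remain in it.

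The derivation algorithms code a lost patient as a failure. Loss is defined as "no survival information at M18 and later" in SAP 10.1 and as "no survival information at M12 and later" in SAP 10.2. Both algorithms also code death for any reason as failure, and the 18-month one ends by sending every unresolved case to failure. The listing in SAP 8.7.2 counts "rescue medication and LTFU" among the signs of failure.

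SAP 5 also defines an Evaluable set. It drops lost patients unless they had already failed, patients with no post-treatment lumbar puncture, and clearly unrelated deaths. SAP 8.6 and 8.7.1 use it for success rates only.

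Model 3 uses a weighted symptom score: sleepiness 5, prurit 4, tremor 3, asthenia 2, headache 1. In Model 4, "the failure rate will be related to the presence of a symptom score of 12 or more". Protocol 4.3 requires of out-patients: "No neurological symptoms".

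**The concern.** Counting unknown outcomes as failures is a defensible, conservative choice for a single-arm success rate. It does not carry over to a model of which patients fail. There, each lost patient or unrelated death enters as an event that may have nothing to do with the drug, and no planned model separates these events from relapse.

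Few failures are expected, so a handful of such events matters. They can hide an association with baseline CSF count, symptoms or leftover tablets, or suggest one that is not there.

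Model 4 has a further difficulty. If only in-patients can reach the cut-off, its contrast is tied to treatment setting, and no cohort term is planned.

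**Working it through.** **1. The plan's own figure.** Protocol 9.1 gives 174 patients for ±5% (Wald) at 87% success. n = 1.96² × 0.87 × 0.13 / 0.05² = 173.8, so 174 reproduces. The expected success of 87% to 91% means 9% to 13% failure: 0.09 × 174 ≈ 16 to 0.13 × 174 ≈ 23 events. The documents give no loss rate. An assumed 5% loss is 0.05 × 174 ≈ 9 patients, which is large beside 16 to 23.

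**2. How mixing acts.** Let p(x) be the probability of true failure at covariate x and l(x) the probability of loss. The probability of being coded a failure is l(x) + (1 − l(x))·p(x). Worked for a two-group contrast with assumed true failure of 8% and 25%:
- True OR = (0.25/0.75)/(0.08/0.92) = 3.83.
- With 5% loss in both groups, the coded rates are 0.05 + 0.95 × 0.08 = 0.126 and 0.05 + 0.95 × 0.25 = 0.2875.
- Coded OR = (0.2875/0.7125)/(0.126/0.874) = 2.80.

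**3. Continuous covariate, loss unrelated to it.** Logistic model, n = 174, standardised log CSF count, Wald test at two-sided 0.05 (SAP 7.2), 1,000 simulated trials per row. True failure, OR per SD and loss rate are all assumptions.

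| True failure | True OR | Loss 2 / 5 / 10%: mITT OR | Power, mITT | Power, lost excluded |
|---|---|---|---|---|
| 5% | 1.5 | 1.34 / 1.23 / 1.15 | 14 / 11 / 10% | 18 / 18 / 19% |
| 8% | 2.0 | 1.75 / 1.54 / 1.37 | 52 / 44 / 33% | 60 / 64 / 60% |
| 13% | 2.0 | 1.83 / 1.66 / 1.50 | 78 / 66 / 54% | 81 / 79 / 78% |
| 13% | 2.5 | 2.21 / 1.94 / 1.68 | 93 / 87 / 80% | 97 / 95 / 94% |

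**4. Loss related to the covariate** (8% true failure, 10% loss):
- Loss rising with CSF count (OR 2 per SD): no true effect appears as OR 1.48 and is significant in 44% of trials, against 4% with lost patients excluded. A true OR of 2.0 appears as 2.08.
- Loss falling with CSF count (OR 0.5 per SD): a true OR of 2.0 appears as 0.93.

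Here loss is independent of failure given x, which is why excluding lost patients works.

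**5. An effect near the Protocol's expectation.** Protocol 9.1 expects success near 92% in early stage and slightly below 89% in late stage, so failure of about 8% against 11% to 12%. Assume ln(CSF count) is N(1.3, 0.6) in 40% of patients (early) and N(4.6, 1.1) in 60% (late). The means differ by 3.3, and an OR of 1.12 to 1.15 per log unit gives about 8% against 11% to 12%. With 10% true failure and 2% to 5% unrelated loss, power over 3,000 simulated trials is about 9% to 15% on the mITT and 11% to 16% with lost patients excluded.

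**6. The Model 4 score.** The maximum is 5 + 4 + 3 + 2 + 1 = 15, so a score of 12 or more may omit at most 3 points. Five of the 32 symptom patterns qualify: those omitting nothing, headache, asthenia, tremor, or headache and asthenia together. All five include sleepiness; without it the maximum is 4 + 3 + 2 + 1 = 10. Protocol 1.2 places sleep disturbances among the neurological signs, and Protocol 4.3 bars neurological symptoms in out-patients.

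**The case against.** A reader might infer that a CSF effect is likely to be missed because of the mITT. The documents do not support that. Power on the mITT reaches 93% with a strong effect and little loss. A large power gap needs a strong effect: under the mixture in step 5, OR 2.0 per log unit with 5% true failure and 5% loss gives about 54% against 80%, but it implies relapse of about 0.7% in early stage against 7.8% in late stage, far from the Protocol's expectation. Near that expectation the small number of failures is the limit, and changing the set recovers little. Loss may also be rare: the SAP definition is narrow, and Protocol 6.7.2 lets the team travel to patients who move.

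Nor can simple dilution be assumed. Some of these failures depend on stage by rule: without a usable 18-month count, a stage 2 patient also needs a 6-month count of at most 50/µL, a condition not stated for the earlier stages (SAP 10.1). Deaths from any cause include HAT deaths.

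These are not the only analyses of who fails. SAP 8.6 gives success rates by cohort, stage and baseline CSF class, though also on the mITT. The listing shows the sign of failure for each patient, so the types can be told apart, but no model uses them.

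On Model 4, one might infer that hospital patients are set against out-patients. The reference group also holds every in-patient scoring below 12. That no out-patient can be exposed depends on recorded sleepiness counting as a neurological symptom. That is plausible but not certain, because HAT symptoms and the neurological examination are collected separately (Protocol 6.2.2).

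What remains is that the models mix outcome types, no model separates them, and a suitable set is already defined.

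**Conclusion.** The point holds as a limitation of secondary models. Models 1 to 4, including Model 2 on leftover tablets, take as failure a mixture of treatment failure and outcomes not known to be treatment failure. The bias is attenuation if the added outcomes are unrelated to the covariate; otherwise its direction is unknown. Its size is conditional on assumed loss rates and effect sizes, so the figures above show a range and do not predict this trial's result.

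The confounding of Model 4 with treatment setting is probable, and is limited to its exposed group.

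This reading takes the loss and death steps of the 18-month algorithm, whose table is broken in the text available, to apply to both stage groups, as the 12-month table appears to do.

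**What to change.** - Fit Models 1 to 4 also on the Evaluable set, or with failure limited to trypanosomes, CSF criteria, rescue for relapse or HAT-related death. In the second case, leave patients of unknown outcome out of the fit; do not recode them as successes. Report the result beside the mITT fit.
- State that the Evaluable fit assumes non-informative loss, since the set is defined by events after baseline. As worded, it also drops anyone with no post-treatment puncture, with no stated exception for a patient who had already failed; the restricted definition of failure avoids this.
- Tabulate failures by type, by cohort and overall.
- Fit Models 3 and 4 in in-patients as well, or add cohort as a covariate, and report how many out-patients score 12 or more.
- In the same edit, name the time point of the modelled outcome, and define or delete Model 5, which SAP 9.1 lists but SAP 8.7.2 does not describe.

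The cost is SAP wording, reruns of simple models and a few extra tables. The refits have fewer events, so intervals may be wide and a null result should not be read as absence of an effect.

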#### Description:

A listing of failures will provide for each failure:

- The time to failure (since the first treatment administration)
- Signs of failure observed: WBC in CSF >20/ $\mu$ L, death (cause if known), presence of trypanosomes in blood or lymph, rescue medication and LTFU
- Number of WBC in CSF at inclusion
- WBC in CSF at inclusion classified as follows:  $\leq$  100, 100-400 and  $>$  400/ $\mu$ L
- Presence of trypanosomes in CSF
- Presence of the following symptoms at inclusion: sleepiness, prurit, tremor, asthenia and headache
- Number of tablets left over at the end of treatment.

#### Statistical modeling: logistic regression

- Model 1: the failure rate will be related to the  $\log_e$  of the number of WBC in CSF (/ $\mu$ L) at inclusion.
- Model 2: the failure rate will be related to the compliance (number of tablets left over at the end of treatment)
- Model 3: the failure rate will be related to the score equal to the sum of weighted symptoms at inclusion (5 points if sleepiness observed at entry, 4 points for prurit, 3 points for tremor, 2 points for asthenia and 1 point for headache).
- Model 4: the failure rate will be related to the presence of a symptom score of 12 or more (see model 3).

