1.2. Clinical Presentation of HAT

There are two successive stages in the clinical course of HAT. In the first stage, called the haemolymphatic or early stage, trypanosomes are present only in the blood and lymphatic system. The clinical signs and symptoms are mild and nonspecific, including bouts of fever, headache, joint pain, itching and lymph node enlargement. Patients diagnosed with early-stage HAT due to T.b. gambiense (g-HAT) receive intramuscular injections of pentamidine for 7 days. If left undiagnosed and untreated, patients progress to the next stage, called the meningoencephalitic stage or late stage, in which parasites invade the central nervous system. At this stage, patients display neurological signs including mental confusion, behavioural changes, sensory disturbances, sleep disturbances and, eventually, coma and death. Patients diagnosed with late-stage HAT are hospitalised for treatment with nifurtimox-effornithine combination therapy (NECT). There is also an intermediate stage in which no parasites are detected in the cerebrospinal fluid (CSF), however the white blood cell count (WBC) in the CSF is between 6 and 20/µL (1, 12, 168). Patients with intermediate-stage HAT can be treated with pentamidine.

Confidential Page 18 of 83

Diagnostic Process for Patients in the Study

HAT due to T.b. gambiense may be diagnosed either in the context of passive screening in patients who present spontaneously to the hospital or to one of the outlying healthcare centres or in the context of active screening by mobile teams or prospections in the field. Whatever the context, the diagnostic process will consistently include the following three steps: screening for potential infection using clinical and serological assessments, detection of the parasite and staging of the disease by lumbar puncture and CSF analysis (see Figure 1).

[figure not shown]

Figure 1 – Decision Tree for the Diagnosis of HAT in the Context of the Study

CATT: Card Agglutination Test for Trypanosomiasis

Tryps: Trypanosomes CSF: Cerebrospinal Fluid WBC: White Blood Cell count Pos: Positive

Neg: Negative

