4.1. Inclusion Criteria

To be included in the study, the patient must fulfil all of the following criteria:

- Male or female patient, including breastfeeding or pregnant women in the second or third trimester;
- ≥ 6 years of age;
- ≥ 20 kg body weight;
- Signed Informed Consent Form and Assent Form for patients less than 18 years of age;
- Trypanosomes detected in any body fluid;
- Physically able to ingest at least one solid meal per day;
- Able to take oral medication;
- Karnofsky Performance Status > 40% (see Appendix 2 Performance Status Scale, p74);
- Able to comply with the schedule of follow-up visits and with the study constraints;
- Easily reachable during the out-patient follow-up period;
- Willing to undergo lumbar punctures.

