**Table 1 : Classification of patients according to stage/severity at inclusion**

Tryps in CSF	WBC in CSF		
	≤ 5/ $\mu$ l	[6-20/ $\mu$ l]	> 20/ $\mu$ l
Tryps in CSF (positive)	Stage 2	Stage 2	Stage 2
No tryps in CSF (negative)	Stage 1	Intermediate stage	Stage 2

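### Model 1 takes the log of the baseline CSF white cell count, which is undefined at 0, an admissible count for which the SAP gives no rule

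*SAP*

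**What the plan says.** SAP 8.7.2 plans four logistic regressions of failure. In Model 1 the covariate is the natural log "of the number of WBC in CSF" per µL at inclusion. No offset, floor or other treatment of a zero count is given.

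The analysis set is stated three times. The opening line of 8.7.2 places the analysis of failures on the mITT overall. The table list in SAP 9.1 titles the output "Logistic regression: Model 1 – all patients (mITT"). SAP Section 5 defines the mITT as "all patients who took at least one tablet of fexinidazole", with no condition on the CSF count.

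Three places bear on whether a zero can occur:

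- SAP Table 1, "Classification of patients according to stage/severity at inclusion", has a lowest class of 5/µL or fewer with no lower bound. A patient in that class is stage 1 if the CSF is free of trypanosomes and stage 2 if it is not. The intermediate stage is 6–20/µL.
- Protocol 4.1 requires "Trypanosomes detected in any body fluid" and sets no minimum CSF count.
- Protocol 1.2 describes early disease as the stage in which "trypanosomes are present only in the blood and lymphatic system", so very low CSF counts are to be expected in a trial open to all stages.

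SAP 7.6 has rules for the outcomes, for adverse event attributes and dates, and for therapy stop dates. It has none for covariates. Section 11 is silent on the point.

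**The concern.** The stated transform fails at a value that the plan itself allows. If a zero occurs, the programmer must either let the record fall out of the model or choose an offset that nobody specified. In the first case the table no longer covers the patients its title claims, and every lost record sits at the bottom of the predictor being studied. In the second case an analyst's choice enters a model that has few events.

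**Working it through.** **The plan's own figure.** No figure is stated for Model 1. The planned sample size serves as the denominator and can be reproduced from Protocol 9.1: n = 1.96² × 0.87 × 0.13 / 0.05² = 173.8, which rounds up to 174. At 87% success, about 0.13 × 174 = 22.6 patients, say 23, would be failures.

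**Where the transform breaks.** The classes in Table 1 run from 5 or fewer straight to 6–20, which implies whole-number counts.

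| Count per µL | ln(WBC) | ln(WBC + 1) |
|---|---|---|
| 0 | undefined | 0 |
| 1 | 0 | 0.69 |
| 5 | 1.61 | 1.79 |
| 20 | 3.00 | 3.04 |
| 100 | 4.61 | 4.62 |
| 400 | 5.99 | 5.99 |

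Only exact zeros fail. An intermediate-stage patient has at least 6 cells and cannot be affected.

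**How many patients.** The documents give neither the stage 1 share nor the share of stage 1 patients with zero cells, so both are assumptions here. Expected loss = 174 × stage 1 share × zero share:

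| Stage 1 share | 5% zeros | 20% zeros | 40% zeros |
|---|---|---|---|
| 20% | 1.7 | 7.0 | 13.9 |
| 40% | 3.5 | 13.9 | 27.8 |
| 60% | 5.2 | 20.9 | 41.8 |

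The N in Model 1 would then lie between about 172 and 132. Zero-count stage 2 patients with trypanosomes in the CSF would add to the loss and are not in this table. The width of the range reflects the assumptions only.

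**Effect on the slope.** An illustrative simulation used 400 replicates of 174 patients, 40% of them stage 1. Stage 1 counts were 1–5 apart from the zero share. Stage 2 counts were log-normal (log mean 4.5, SD 1.2). The logit of failure was −3.6 + 0.4 × ln(WBC + 1). Median fitted slopes were:

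| Zeros among stage 1 | Dropped | Offset 0.1 | Offset 0.5 | Offset 1 |
|---|---|---|---|---|
| 5% | 0.36 | 0.37 | 0.38 | 0.39 |
| 20% | 0.40 | 0.37 | 0.40 | 0.41 |
| 40% | 0.40 | 0.34 | 0.38 | 0.40 |

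Dropping zeros moves the slope little. The choice of offset moves it by about as much or more. The true relation was set on the +1 scale, so these results do not show that +1 is the right offset.

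**What an offset does at the low end.** A zero count is placed at ln(0.1) = −2.30, ln(0.5) = −0.69 or ln(1) = 0. The distance between 1 and 5 cells is ln(5) = 1.61 with no offset, ln(5.5/1.5) = 1.30 with 0.5, and ln(6/2) = 1.10 with 1.

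**The case against.** The case on the other side is largely about size, and much of it stands.

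- The documents do not show that any baseline count is 0, or how an empty counting chamber is recorded. SAP 7.1 names SAS but no procedure. Deletion is the ordinary default and is inferred here. The point is therefore conditional on a zero occurring.
- Model 1 is a secondary model that does not appear among the protocol's effectiveness analyses. SAP 8.6 also reports the 18-month outcome by stage and by CSF count class on the mITT, and zero-count patients stay in those tables.
- SAP Section 12 requires derived variables to be validated, exhaustively where possible. A missing log beside a recorded 0 should be noticed there. That makes silent loss less likely, but it does not supply a rule.
- The offset of 1 is a convention, and a floor or another offset could be defended.

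A reader might infer three stronger things, none of which the documents support:

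- **Only stage 1 patients are at risk.** Table 1 also allows 0 cells in stage 2 when trypanosomes are in the CSF.
- **The lost patients are those least likely to fail.** Protocol 9.1 puts success near 92% in early-stage patients and slightly below 89% in late-stage patients. Protocol 9.5.3 expects slightly higher success in late-stage patients. The two sections conflict, and deaths from any cause and losses to follow-up also count as failures.
- **A sizeable and known share of the trial is lost.** No such share can be computed from the documents.

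**Conclusion.** The point holds as a minor one. This is a stated rule that breaks at an admissible value, which goes beyond a missing detail: if any baseline count is 0, Model 1 as written cannot be fitted to the set it is labelled with. The number of patients affected is unknown and may be very small. The range of about 2 to 42 of 174 rests wholly on assumed shares. The expected bias in the slope is modest. The harm lies mainly in an undeclared change of analysis set or an offset chosen without pre-specification. The primary success rate and its exact confidence interval are not touched.

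**What to change.** In SAP 8.7.2, define the Model 1 covariate as ln(WBC + 1), with WBC the baseline CSF count per µL, for all mITT patients with a recorded baseline count. Under the table, report the number of zero counts and the N used. List the change in SAP Section 11. That section already records a change made after database lock, so if this one is also made after lock, say so.

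The cost is one term in the model and one entry in Section 11. Counts of 100 and above hardly move. The small downside is that the offset is a convention that slightly compresses the 1–5 cell range, so a check with another offset, for example 0.5, can be shown beside the main fit. The offset does nothing for a patient whose baseline count is missing altogether, which is another reason to report the N.
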